Profiling the vaginal and seminal microbiome and human virome in a smaller cohort of patients going through their first IVF cycle is an exploratory portion of this study. Existing studies are limited and conflicting regarding influence of the microbiome on IVF cycle outcomes.¹¹⁻¹³ This would be the first study to evaluate alterations in the reproductive tract microbiome across the IVF cycle in response to medications and supraphysiologic hormone levels, and the first to evaluate the human virome in this patient population.^{6,7} We would examine differences within and between groups and assess for the potential impact and association clinical outcomes of those patients exposed to prophylactic azithromycin, and those who are not. Optimizing the vaginal microbiome could serve as a potential target for therapy to help increase IVF success rates in the future with the goal of a full term, live birth.

C Study Objectives

C1 Primary Aim

Specific Aim 1: Determine the effect of withholding prophylactic antibiotic administration on clinical pregnancy rate (defined as a gestational sac, with fetal pole and cardiac activity, on ultrasound).

We *hypothesize* that withholding prophylactic antibiotics before embryo transfer will be non-inferior (absolute difference $\leq 15\%$) to routine prophylaxis in terms of clinical pregnancy rates.

C2 Secondary Aim

Specific Aim 2: Evaluate the impact of prophylactic antibiotic administration on miscarriage rate (pregnancy loss per clinical pregnancy) before 20 weeks.

Our *working hypothesis* is that miscarriage rates will be equivalent between the two groups.

Specific Aim 3: Determine the effect of no prophylactic antibiotic administration on embryo development.

We *hypothesize* that embryo development, as evaluated by fertilization rate (number of two-pronuclei embryos per mature oocyte), blastocyst conversion rate (number of day 5 embryos from two-pronuclei embryos), and blastocyst utilization rate (number of day 5 embryos transferred or frozen per two-pronuclei embryos) will be equivalent between the two groups.

Specific Aim 4: Determine the impact of prophylactic antibiotics or withholding prophylaxis on the vaginal and endometrial microbiome.

We *hypothesize* that azithromycin will impact the vaginal microbiome. Additionally, we expect to see changes across the IVF cycle that may be associated with cycle outcome endpoints.

Specific Aim 5: Evaluate the implications of the human virome on IVF outcomes.

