Azithromycin is routinely given to both partners (in male/female couples) or to the embryo recipient in same sex couples or gestational carriers when they start their IVF cycle medications and is our current standard of care.

3.b Treatment Regimen

1 gram oral azithromycin, once the day of IVF cycle start (when they start injectable gonadotropin medications) which is our current standard of care.

3.c Method for Assigning Subjects to Treatment Groups

Computer random number generator.

3.d Preparation and Administration of Study Drug

Azithromycine will be prepared and dispensed by the patients preferred pharmacy as is standard practice if they are randomized to the antibiotic prophylaxis group.

3.e Subject Compliance Monitoring

Patients will give verbal confirmation of compliance.

3.f Blinding of Study Drug

Patients will not be blinded to which group they're in. A placebo control will not be used.

3.g Receiving, Storage, Dispensing and Return

Azithromycin will be prepared and dispensed by the patients preferred pharmacy as is standard practice if they are randomized to the antibiotic prophylaxis group.

E Study Procedures

E1 Screening for Eligibility

Couples will be screened for eligibility by their primary physician, the primary investigator, [name] or the Research Project Coordinator. If they meet the inclusion and exclusion criteria they will be offered enrollment.

E2 Schedule of Measurements

Outcomes measures are routinely tracked by our clinical to report to the Society of Assisted Reproductive Technology (SART). Patients who participate in the study will not be required to make any additional visits beyond consent.

E3 Visit 1

Outcome measures for specific aim 3 will be tracked from the patients initial oocyte retrieval and embryo transfer visit. The lab routinely tracks this data and no additional query or visits will be required in term of embryo development data.

E4 Visit 2 etc.

Specific Aim 1 will be addressed and tracked when patients come in for their viability ultrasound at 6-7 weeks gestation which is routine practice in our clinic. Clinical pregnancy is defined as a gestational sac, with fetal pole and cardiac activity, on

ultrasound. No additional visits will be required. Patients will continue to be tracked once they are released from our practice to their primary OBGYN to track miscarriage rate (spontaneous loss prior to 20 weeks) and subsequent live birth outcomes.

Schedule of Visits for Microbiome/Virome Study:

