Given the conflicting evidence toward benefit of routine antibiotic prophylaxis and IVF outcomes, a non-inferiority approach was selected to test our hypothesis that no prophylaxis is not inferior to routine antibiotic administration. A total sample size of 356 patients (178 per arm) was determined based on an average baseline clinical pregnancy rate of 41% within our practice in this population with a non-inferiority margin of 15%, 80% power, and using a one sided $\alpha=0.025$ while estimating a 5% drop out rate. Our practice completed approximately 500 fresh IVF cycles in 2016. Our exclusion criteria are broad and we do not anticipate patient recruitment to be difficult. We believe 356 patients is feasible and estimate a 14 month timeline to complete recruitment if we enroll 7 patients at minimum per week.

F2 Interim Monitoring and Early Stopping

Interim analysis will be performed according to the Haybittle-Peto approach at 50% enrollment and 75% enrollment. This study will be considered safe to continue if there is an absence in trend toward severe adverse maternal, pregnancy or laboratory outcomes in either group. The DSMB will also assess recruitment progress and will review for futility of the trial in the context of lack of adequate recruitment. Data will be formally analyzed at 50% enrollment and then every 6 months thereafter to assess for early termination of the study.

F3 Analysis Plan

See Table 1 for timetable of patient enrollment and analysis. Our practice is required to track patient demographic data and cycle outcome measures to report to the Society for Assisted Reproductive Technology. Data are recorded and tracked through Research Electronic Data Capture (REDCap). Data from enrolled patients will be exported and tracked in a separate secure REDCap dataset from our existing dataset. All of our outcome measures are routinely tracked, and no additional data query will be required to address potential confounders as listed in Table 2.

F4 Statistical Methods

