Intention-to-treat and per protocol analyses will be performed. Chi-squared and Fisher's exact tests will be used to compare categorical variables as appropriate. Kolmogorov-Smirnov test will be initially used to assess the distribution pattern of continuous variables. Normally distributed variables will be analyzed via Student's t-test. Non-normally distributed continuous variables will be analyzed with the Mann-Whitney U test. The primary analysis is based on difference in clinical pregnancy rate between the two groups. The sample size estimation for the study is based on this comparison with a non-inferiority approach as described above with an absolute difference of 15% or less to be considered non-inferior. Secondary analyses will include spontaneous miscarriage rate and embryo development. A subsequent interval analysis will assess live birth rate. Pearson's correlation coefficients will be used to quantify the association

between the two groups and embryo development. $P < 0.05$ will be considered statistically significant.

Each microbiota sample will have the taxon indicated as relative abundance. To assess the diversity across an IVF cycle, after log transformation, linear mixed regression will be applied. Wilcoxon rank sum will be used to measure for difference in richness and diversity with clinical outcomes of clinical pregnancy rate, miscarriage rate and embryo outcomes.

IBM® SPSS® statistics version 23 will be used for all analyses.

F5 Missing Outcome Data

All outcome data is required to be tracked by SART and no additional query will be required. We do not anticipate any issues with missing outcome data.

G Data Handling and Record Keeping

G1 Confidentiality and Security

Our practice is required to track patient demographic data and cycle outcome measures to report to the Society for Assisted Reproductive Technology (SART). Data is currently recorded and tracked through Research Electronic Data Capture (REDCap). REDCap is a secure web-based application designed to support data capture for research studies, providing 1) an intuitive interface for validated data entry; 2) audit trails for tracking data manipulation and export procedures; 3) automated export procedures for seamless data downloads to common statistical packages; and 4) procedures for importing data from external sources.¹⁸ Enrolled patients will be exported and tracked in a separate REDCap data set from our existing dataset.

G2 Records Retention

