Study records will be stored and tracked through REDCap as noted in G1. Signed consents will be kept in a locked cabinet in a locked office. Data will be retained until study enrollment and analysis is complete.

H Study Administration

H1 Organization and Participating Centers

Washington University Department of Reproductive Endocrinology and Infertility.

H2 Funding Source and Conflicts of Interest

The PI, [name] is a recipient of funding from NIH 5T32HD055172 as a part of her Masters of Science and Clinical Investigation clinical research track. There are no conflicts of interest to report.

H3 Subject Stipends or Payments

Not applicable.

H4 Study Timetable

See Table 1.

I Publication Plan

We plan on presenting our findings at national meetings including those for American Society for Reproductive Medicine and Society for Reproductive Investigations. We plan to publish our results in journals that have a high impact among reproductive endocrinologists within 6 months of completing our data collection.

J Attachments

J1 Tables

Figure 1: Timetable (months)

	1	2	3	4	5	6	7	8	9	10	11	12	13	14	15	16	17	18	19	
Patient Recruitment	X	X	X	X	X	X	X	X	X	X	X	X	X	X						
Analysis															X	X	X			
Manuscript Composition																	X	X	X	

Table 2. Potential confounders

Patient history	Cycle level factors	Cycle outcome
-----------------	---------------------	---------------

Demographic data: Maternal age, race, ethnicity Medical history: BMI, tobacco use Obstetric history: gravidity, parity Infertility diagnosis Duration of infertility Number of prior IVF cycles Baseline labs: Follicle stimulating hormone or antimullerian hormone level, antral follicle count	Total amount of gonadotropin administered Stimulation protocol Number oocytes collected Number mature oocytes Insemination method (conventional vs. intracyto-plasmic sperm injection [ICSI] vs. partial ICSI) Number oocytes normally fertilized (two pronuclei) Day of embryo transfer Number of embryos transferred Number of embryos frozen	Clinical pregnancy rate Spontaneous miscarriage rate Live birth rate
---	---	--

K References

1. www.sart.org
2. Czernobilsky B. Endometritis and infertility. *Fertil Steril.* 1978;30:119-130.

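### The drawn timetable closes analysis about 1.6 months before the last pregnancies can reach 20 weeks, and no data cut is set for miscarriage (Aim 2)

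*Combined protocol and SAP*

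**What the plan says.** - **Timetable.** Section F3 sends the reader to it: "See Table 1 for timetable of patient enrollment and analysis". It is printed in J1 under the label "Figure 1: Timetable (months". It marks recruitment in months 1–14, analysis in months 15, 16 and 17, and manuscript work in months 17–19.
- **Recruitment.** F1 says the investigators "estimate a 14 month timeline to complete recruitment if we enroll 7 patients at minimum per week".
- **Outcome.** Aim 2 in C2 concerns "miscarriage rate (pregnancy loss per clinical pregnancy) before 20 weeks". E4 says that patients are followed after release to their obstetrician "to track miscarriage rate (spontaneous loss prior to 20 weeks) and subsequent live birth outcomes".
- **Which analysis comes when.** F4 states: "Secondary analyses will include spontaneous miscarriage rate and embryo development". It then treats one outcome separately: "A subsequent interval analysis will assess live birth rate".
- **Silent points.** No section gives a data cut, a censoring rule or a maturity condition for miscarriage. F5 expects no problem with missing outcome data.

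**The concern.** A loss-before-20-weeks outcome is complete only when every clinical pregnancy has either ended or passed 20 weeks. The chart leaves no time for that between the last recruitment and the analysis. F4 recognises that live birth needs longer follow-up and gives it a later analysis, but leaves miscarriage with the outcomes that mature early.

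If the printed schedule is followed, some pregnancies will still be in progress at the cut. The chi-squared and Fisher tests in F4 need each pregnancy classed as a loss or not. Classing an ongoing pregnancy as not lost lowers the rate in both arms and shrinks any absolute difference between them. That moves the result toward the plan's working hypothesis that the arms are equivalent on miscarriage. The same event is also listed as a severe adverse event in E5 (5.c), so an undercount is undesirable on safety grounds too.

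**Working it through.** **Inputs from the plan.** 356 couples, 178 per arm; 41% clinical pregnancy rate; 15-point margin; one-sided alpha 0.025; 80% power; 5% dropout; 14 months' recruitment; at least 7 per week (all F1). Analysis in months 15–17 (J1). Viability scan at 6–7 weeks (E4). Loss before 20 weeks (C2, E4).

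**Assumptions.** The plan gives no lag from recruitment to 20 weeks' gestation. I take 20 weeks and show 18–24. Accrual is even over 14 months. One month is 365.25/12/7 = 4.348 weeks.

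**1. The plan's own figures.**
- Sample size: (1.960 + 0.842)² × 2 × 0.41 × 0.59 / 0.15² = 169 per arm, and 169/0.95 = 178. This reproduces.
- Recruitment time: 356/7 = 50.9 weeks, or 50.9/4.348 = 11.7 months. This does not reproduce the stated 14 months, which corresponds to 356/(14 × 4.348) = 5.8 per week.

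**2. When the last couple reaches 20 weeks, on 14-month recruitment.**
- 20/4.348 = 4.60 months, so 14 + 4.60 = month 18.6. That is 18.6 − 17 = 1.6 months after the analysis window closes.
- For a lag of 18 weeks: 14 + 4.14 = 18.1. For 24 weeks: 14 + 5.52 = 19.5.
- A couple recruited at the start of month 14 gets there at 13 + 4.60 = 17.6, also too late.

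**3. The earliest sensible cut.** The last couple's 7-week scan falls at 14 + 7/4.348 = month 15.6. Before that, neither the primary outcome nor the denominator of Aim 2 is complete.

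**4. Share of couples short of 20 weeks.** Share = (14 − (cut − 4.60))/14.
- Cut at 15.6: (14 − 11.0)/14 = 21%.
- Cut at 17.0: (14 − 12.4)/14 = 11.4%, about 41 of 356 couples (29 to 64 for a lag of 18–24 weeks). At 41% pregnant, that is about 17 of 0.41 × 356 = 146 clinical pregnancies.

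**5. Share of losses missed.** This assumes that ongoing pregnancies are counted as non-events and that losses are spread evenly over weeks 7–20, a 13-week window. The plan gives no distribution.
- Cut at 15.6: incomplete couples lie between week 7 and week 20, so on average half the window is unseen. 0.21 × 0.50 = about 11% missed. A true 10-point difference appears as about 8.9.
- Cut at 17.0: the latest couple is at 3.0 × 4.348 = week 13. The mean unseen part is (20 − 13)/2 = 3.5 weeks, and 3.5/13 = 27%. 0.114 × 0.27 = about 3% missed. A true 10-point difference appears as about 9.7.
- In counts at month 17, with an assumed miscarriage rate of 10–20% (not in the plan): 146 × 0.10 × 0.03 to 146 × 0.20 × 0.03, about 0.4 to 0.9 losses missed across both arms.

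**6. The same check at 7 per week.** 11.7 + 4.60 = month 16.3, inside the window as drawn. With a 24-week lag it would be 11.7 + 5.52 = month 17.2, just outside.

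**The case against.** The strongest reply is that the plan nowhere says miscarriage will be analysed on immature data. A reader might infer from the chart that the sponsor intends a truncated analysis with ongoing pregnancies counted as non-events. The documents do not support that: C2 and E4 define the outcome to 20 weeks, E4 promises continued tracking, and section I counts publication from the end of data collection. Honouring the definition would make the timetable slip rather than cut the data. Figure 1 is also plainly a coarse chart. It shows no slot for live birth, which would fall near month 23 for the last couple (14 + 40/4.348 = 23.2). This stands, and it makes the truncation conditional on the timetable being kept.

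A reader might also take the opening of the analysis window as the cut and conclude that a third of couples (4.60/14 = 33%) would lack follow-up. That does not stand, because at month 14 the last viability scans would not have been done. Nor is it fair to assume that no losses are seen in couples short of 20 weeks. By the end of month 17 all of them would have passed about week 13.

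The 7-per-week rate is a partial answer. It would largely remove the shortfall, but it contradicts the 14 months that F1 states and J1 draws, so it cannot be relied on until the two are reconciled.

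None of this removes the conflict. The schedule that F3 points to cannot deliver complete Aim 2 data on 14-month recruitment, and nothing in the plan says which gives way.

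**Conclusion.** The point holds as a scheduling conflict with a missing data cut, not as a stated intention to truncate. The shortfall persists across the assumed 18–24 week lags, at 1.1 to 2.5 months past month 17. Any consent-to-cycle-start delay beyond the assumed lag would widen it.

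The likely consequence is small. Even at the earliest sensible cut, roughly a tenth of losses would be missed, falling to a few per cent by the end of month 17. These figures rest on even accrual, an even spread of losses over weeks 7–20, and ongoing pregnancies being scored as non-events, none of which the plan specifies. The issue is confined to a secondary outcome. The primary outcome is complete by about month 15.6 and is unaffected. It is still worth correcting, because any error runs toward the hypothesised result and the remedy is cheap.

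**What to change.** - State in F4 that the Aim 2 data cut is the date on which the last clinical pregnancy has ended or reached 20 weeks. Move that analysis in Figure 1 to about month 19. The primary analysis keeps its place.
- If miscarriage must be reported earlier, include couples by cycle start date only, whatever their outcome: for a month-17 cut, those who started by about month 12.4 (17 − 4.60). Restricting by date avoids keeping early losses from late starters while dropping their ongoing pregnancies.
- Reconcile the 7-per-week rate with the 14-month recruitment period in F1 and Figure 1, and set the cut from the reconciled figure.

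The cost is about two months' delay to one secondary analysis. No extra visits are needed, since E4 already plans to follow these pregnancies.
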